### 5.2.3 Blinding

Participants, the interventionist and the PI will be aware of the participants' treatment assignments. However, data collectors will be blinded.

### 5.3 Intervention

The 8-week intervention will consist of four components. After the intervention, the intervention group will keep their Fitbit and the HidrateSpark smart water bottle.

### 5.3.1 Instructional/goal setting session

The study team member will provide an orientation at the baseline visit 2. The study team member will review the activPAL data and identify targetable prolonged SB bouts. The study team member and the participant will set two goals:

1) a SB reduction goal will be set as reducing daily sedentary time gradually until they reach the goal of  $\ge$  120 minutes SB reduction; and 2) a sedentary break goal will be set as 3 minutes of standing/walking every 1 hour and then increasing its duration to 5 minutes and its frequency to every 30 minutes.

These goals were feasible in stroke patients and T2D patients. The participant will enter the goal into the Fitbit for self-monitoring and fill out the first worksheet in the Ten Top Tips (TTT). The TTT is a booklet developed from the Habit Formation Theory and includes 10 tips to add SB breaks into their daily routine. The ten tips are modified to eight in our study. See Appendix for the TTT and worksheet. This goal session will last approximately 1 hour.

### 5.3.2 Fitbit

Intervention group participants' Fitbits will be programmed to provide the 'Reminder to Move' or 'Move Alert'. The move alert is a notification that cues the participant to walk at least 250 steps per hour. The Fitbit will vibrate when they have been sitting for 60 minutes. Participants can select the days and the time ranges to receive the move alerts. Patients will be encouraged to review their daily summary before they go to bed.

### 5.3.3 Smart Water Bottle

We will provide a HidrateSpark water bottle, and the study team member will assist participants in downloading the app and creating an account. The study team member will instruct participants on how to use the bottle, with the official user manual. The device alerts participants with a color change and message on the Fitbit to keep them hydrated. The device provides the daily water intake summary in the Fitbit app. We will advise participants to drink 4.5 – 6 bottles (500ml/bottle) of water per day based on current recommendations by the U.S. National Academies of Medicine. The HidrateSpark accounts require a unique email address for each user and the same email which is used to Fitbit account will be used to the HidrateSpark app. The same rules will be applied to the HidrateSpark account, and the account information will be stored in protected PI's computer within encrypted documents. Once the intervention is concluded, HidrateSpark data will not be collected. Also, the HidrateSpark bottle and the app will be reset for the participant to keep using the bottle.

### 5.3.4 Text Messages

Date: May 15th, 2024

Text messages will be provided to support and enhance the habit formation process. Text messaging has shown effectiveness in many exercise studies. There are three weekly default text messages which will be sent. Participants will also receive up to one text message per day providing a daily tip, which will be tailored to participants based on preferred message frequency and activity choices. In addition, the interventionist will offer weekly personalized feedback on the participant's progress towards goal achievement and helpful tips. The first default text message will be sent on Thursday to provide feedback on their progress for the week. The second default text message will be sent on Saturday morning to encourage them to sync their Fitbit to the Fitbit app.

The third text message will be sent on Monday morning to prompt participants to report their weekly activity. Participants will be instructed to open their Fitbit app, tap on 'Hourly Activity', and navigate to their data from the previous week. They will then respond to the survey text message with their average daily active hours from the previous week. Based on the participants' responses, the interventionist will propose an adjustment to the goal, either by suggesting a new lower goal or recommending the same goal. Participants will then respond to either accept the proposal or reject it. They will also get an introductory video explaining Fitbit app navigation.

When participants take an SMS survey, questions are asked one at a time as an SMS text message conversation/thread. We will ask three questions (three SMS text messages). Participants may respond with any kind of alpha-numeric text for SMS survey. Only REDCap administrators are allowed to enable the Twilio option to initiate a survey as an SMS conversation. All messages and Fitbit data will be managed in REDCap. After week 6, participants will set a new goal with the interventionist as part of the mid-program counseling session (described below, in 5.3.5 Mid-Program Counseling Session).

Below is the process of developing and providing text messages:

- 1. Creation of weekly text message template: [name] (Co-I), an expert in effective health communication, and the PI co-created the weekly message template with [name].
- 2. Fitbit data transfer: We will transfer the Fitbit data from the participants' Fitbit accounts to REDCap by developing our own data collection interface using Fitbit's Web Application Programming Interface (API). This platform provides

secure data acquisition and management tools that facilitate remote data collection from Fitbit without the need for study participants to return the devices to researchers for data extraction.

- 3. Integration of Fitbit data into the text message template. The collected Fitbit data from REDCap will be integrated into our weekly text message template.
- 4. Send text messages using Twilio and Redcap. The customized text message will be sent using the Twilio plug-in for REDCap. Twilio module enables our study to make and receive SMS text messages, both to and from study participants. A REDCap and Twilio account are linked together. When a user indicates that an SMS (text) or a call should be sent to a cell phone, REDCap requests that action through Twilio. When a user responds, Twilio relays that information back to REDCap. The data is stored in the REDCap database. Twilio does not store any data, nor does it keep a log of its actions.

### 5.3.5 Mid-Program Counseling Session

At the halfway point of the intervention (after week 4), a focused counseling session will be conducted to re-evaluate and adjust the participants' activity patterns and sedentary break schedules. This interventionist-assisted session represents a critical touchpoint in the intervention, offering participants an opportunity to recalibrate their targets and enhance the positive behavioral changes initiated in the program. The session is outlined as follows:

- Prior to the scheduled Zoom meeting, study participants will be mailed an activPAL device to their home address. Instructions will be provided to participants to ensure correct usage of the activPAL device, which they will wear for a period of one week. Participants will be informed of the procedures for returning the device using a prepaid express mail envelope for overnight shipping.
- Upon receipt of the returned activPAL devices, the study team will promptly download and analyze the collected data. The interventionist will then utilize the data from the activPAL to assess the participant's activity patterns during the mid-program review.
- 3. During the Zoom meeting, the interventionist and participant will review the activity data together. The interventionist will facilitate a discussion to reflect on the participant's progress and challenges encountered in meeting the established goals. Personalized feedback will be provided, and the sedentary break schedules

will be adjusted based on the insights from the activPAL data. Goals and expectations for the remainder of the program will be discussed, reset, and agreed upon, ensuring they are realistic and achievable for the participant. Participants will be encouraged to incorporate the revised goals into their daily routine using their Fitbit for self-monitoring.

4. The audio will be recorded to guarantee consistent adherence to the protocol and to maintain inter-rater reliability among the interventionists. The audio recorded files and transcripts will be saved in the secured computer at a locked office.

# 5.3.6 Control Group

The control group will receive the American Heart Association's Healthy Living booklet. Control group participants will receive all study assessment but will not be instructed to monitor sitting time. The Fitbit move alert setting will be disabled for the control group.

### **5.4 Post-Intervention Visit**

After 8 weeks, all participants will be invited to an in-person visit (post-intervention visit). During the visit, all the above parameters will be re-measured by the same trained research staff. The visit will take about 1 hour including the completion of a series of questionnaires (which participants may complete beforehand) and biometric assessments. All participants will wear the activPAL3 and the CGM for 7 days to examine their post-intervention activity and glycemic control. They will return the devices via prepaid mail. All participants will receive \$50 for the post intervention visit, and an additional \$50 for mailing back the devices to the study team.

Therefore, total compensation would be \$150 for each participant. Also, all participants will be informed of their 24-hour glucose results and activity patterns retrieved from the activPAL device.

### 1. Questionnaires

Participants will answer the same questions about their demographics, socioeconomic characteristics, medical history and current medication, health behaviors, and patient-centered outcomes (e.g., confidence in reducing SB and increasing PA, habit strength for SB, quality of life, and diabetes selfmanagement). Participants will have a choice to complete these questionnaires during the post-intervention visit in person or to receive paper copies of the questionnaires by mail. Printed copies will be identified by the participant's

REDCap record ID number; there will be no additional identifying information on the printed questionnaires. If a participant chooses to receive the questionnaires by mail, he or she will be asked to complete them using a blue or black ink pen no sooner than 2 days prior to their scheduled post-intervention visit and will bring the completed surveys to their post-intervention visit. After the postintervention visit is completed, the study team will enter their responses manually into REDCap and upload a scanned PDF version of the paper questionnaires to their REDCap record. Paper copies of the surveys will be kept in a locked cabinet in the study team's office at the Vanderbilt School of Nursing. Alternatively, participants may opt to receive an email invitation that contains a unique link to a REDCap survey. REDCap ensures that all data transmitted during the survey completion process is secure and that participant privacy is maintained. The system is compliant with standards for sensitive data, such as HIPAA in the United States. In addition, participants will answer questions (Table 2) about feasibility and acceptability of the intervention. Level of satisfaction with the intervention will be assessed by using 23 items from the questionnaire developed by Lyons, Swartz, Lewis, Martinez and Jennings and Burner, Zhang, Terp, Bench, Lee, Lam, Torres, Menchine and Arora. We will also use the 10-item System Usability Scale to assess usability. The scale is considered as "industry standard" and provides a global measure of satisfaction.

#### 2. Biometric Assessment

Participants will undergo the same physical examination (e.g., height, weight, blood pressure, hip circumference, waist circumference). The same protocol and instruments will be used.

#### 3. activPAL data download

The 7 days of activPAL data will be downloaded and stored in the PI's computer.

# 6.0 Reporting of Adverse Events or Unanticipated Problems involving Risk to Participants or Others

### Consent

For the pre-screening activity, potential participants recruited from the email distribution list will sign an e-consent in REDCap. Participants will be given information about what questions we will ask. There are no benefits or side effects related to this prescreening activity. Once they meet all the eligibility criteria, they will be invited for

the in-person baseline visit. At the visit, participants are given as much time as they would like to consider participation from the initial invitation to participate until they sign the "main" consent form. Participants are encouraged to ask as many questions as possible and reminded that participation is completely voluntary and will not affect their medical rights. They are also told that they have the option to discontinue participation at any time for any reason.

### Finger Prick Random Blood Glucose Test

Risks associated with the finger prick include temporary discomfort from the needle prick, bruising, and rarely (<1%) infection. These risks will be minimized by using a sterile technique and applying sustained pressure to the site.

### activPAL

The activPAL activity tracker is a safe, non-invasive method to capture information about activity cycles. Participation in this study requires that participants wear an activPAL tracker adhered (using Tegaderm adhesive dressing) to the front of the right thigh during waking hours for a minimum of 7 consecutive days (baseline and follow-up). The Tegaderm adhesive dressing used to apply the activPAL devices is hypoallergenic and consists of a dual layer hydrogel that does not pull at the skin or hair. There are few risks associated with wearing the activPAL device and include slight discomfort, such as light pressure from the activPAL or irritation from the waterproof dressing.

### **Continuous Glucose Monitor**

The FreeStyle Libre Pro Flash Glucose Monitoring System is an FDA-approved, professional continuous glucose monitoring device indicated for detecting trends and tracking patterns in persons (age 18 and older) with diabetes. After application of the sensor, only a thin, flexible filament will remain under the skin and the sensor is held in place by an adhesive. The following are possible adverse effects of inserting a sensor and wearing the adhesive patch: local erythema (redness), local infection, inflammation, pain or discomfort, bleeding at the glucose sensor insertion site, bruising, itching, scarring or skin discoloration, and adhesive irritation. There is a remote risk of sensor or needle fracture during insertion, wear or removal, with fragments retained under the skin.

### Fitbit

Participants will wear an additional wrist-worn activity tracker for 8 weeks during waking hours. There are few risks associated with wearing the device and include slight discomfort, such as light pressure from the wristband or irritation from wearing a damp band after showering or swimming. There is a possible risk of confidentiality loss. To reduce the risk, we will create an anonymous email account for the Fitbit app. All identifiable data will be kept on password-protected computer systems in a locked office.

### Smart Water bottle

Participants will use the smart water bottle to increase the frequency of standing and moving by frequently going to the restroom and kitchen for refills. There is no risk associated with using the smart water bottle. To reduce the possible risk of confidentiality loss, we will create an anonymous email account for the HidrateSpark app. All identifiable data will be kept on password-protected computer systems in a locked office.

### 8-Week Sedentary Behavior Intervention

Participants will gradually decrease their sedentary behavior and replace the sedentary behavior with a short period of light intensity physical activity such as 2 to 3 minutes of standing or walking over 8 weeks. While participating in this intervention, there is a potential risk of experiencing physical discomfort or symptoms that may include back pain, muscle ache, knee pain, and other discomforts arising from increased activity levels. Additionally, participants may also experience annoyance or inconvenience associated with receiving the tailored text messages. These symptoms or discomforts may occur during the course of the study, but the study team will take measures to minimize any adverse effects and ensure participants' safety and well-being throughout the research process. The level of risk associated with these symptoms or the risk of falling or injury is similar to the risks associated with day-to-day activity. Trained research staff members will instruct participants to make sure there are no hazards within the walking path and surrounding area.

### Suicidal ideation or severe distress

Research has confirmed that simply asking a participant about whether they have thoughts of suicide is not a likely trigger of such an event. It is usually only when the

person reports ideation as well as an intent, plan, and/or means to commit suicide that risk for immediate suicide is considered to be more acute.

If a participant reports severe distress or suicidal ideation during the survey administration (Baseline visit 2 or Post-intervention visit), the research staff will immediately notify the PI. The PI will provide the participant with help to get treatment. This may include:

- working with the participant to contact his/her doctor,
- contacting a trusted family member, or a therapist to discuss his/her thoughts,
- or working with the participant on a plan that may include getting him/her to a hospital for safety.

### 7.0 Study Withdrawal/Discontinuation

Taking part in this study is voluntary, and the participant has the right to refuse to take part in the study. The participant can withdraw from the study at any period and should notify the PI or a study staff member. The decision to withdraw will not affect the participant's ability to get healthcare at the institution, or their enrollment in any health plans or benefits. The investigator may decide to discontinue a participant's participation without permission because she may decide that staying in the study will be harmful for the participant, or the sponsor may stop the study. A participant's decision to withdraw from this study will not be retroactive. For example, if a participant provides consent and completes the baseline visit but then decides to withdraw from the study at the postintervention visit, the data collected from the baseline visit, which was collected in good faith, will not be destroyed.

### **Criteria for Discontinuation of Individual Participants**

Subjects can decide to discontinue entirely from the study at any time for any reason. Subjects can also be discontinued from the study or discontinued from the study treatment due to Investigator decision as detailed below.

- 1. Withdrawal of consent.
- 2. At the Investigator's discretion in certain situations such as lack of compliance or serious adverse event.
- 3. One DKA event or one episode of hyperglycemic, hyperosmolar nonketotic syndrome (HHNS)

- 4. Dangerous hypoglycemia (glucose <54mg/dl after three treatments or unable to function due to low blood glucose during study visits)
- 5. Continuous hyperglycemia (random blood glucose >300mg/dl two times in a row during study visits)

### Protocol for hypoglycemia

During any study visits, if the study participant develops any of the symptoms below, the study team member will check glucose levels immediately. The symptoms are

- Weakness and tiredness
- Sweating
- Fast breathing
- Shakiness, nervousness, and or anxiety
- Nausea
- Confusion and problems communicating
- Light-headedness, dizziness

If the glucose level is below 70mg/dl, one of the following options will be administered.

- 1. 2 oz (60ml) juice
- 2. 15mg of glucose tables

After 15 minutes, the study team member will re-check glucose level. If the glucose level is still below 70mg/dl, the treatment will be repeated up to 2 times.

If the participant's glucose level is still below 70mg/dl after three treatments, the study team member will notify the PI and ask participants to call healthcare provider. If the participant's glucose level is still below 54mg/dl or the participant is unable to function because of mental or physical changes due to low blood glucose, call 911 immediately and notify the PI.

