### **5.0 Study Procedures**

### 5.1 Baseline visit 1: Initial contact, screening, and consent

Interested respondents will be screened by a trained research staff over the phone or inperson, depending on the recruitment methods. For this research, no aspect of the participant's diabetes treatment regimen will be modified.

Those who are eligible for the study will be invited to the in-person visit. The first visit (i.e., Baseline visit 1) will be conducted at VUSN (Vanderbilt School of Nursing)'s lab at Wesley building.

At the Baseline visit 1, individuals will check their blood glucose level via finger prick. If their random glucose levels are between 80-300, they will complete the informed consent with assistance from the trained research staff. The trained research staff will complete baseline biometric assessment, including measure of height, weight, waist circumference, and blood pressure. Those who are consented will participate in: 1) completing survey questionnaires (30 minutes), 2) a baseline biometric assessment, 3) brief instruction regarding the wear of activPAL and continuous glucose monitoring (CGM) devices (30minutes), and 4) start to wear two devices for 7 days. The activPAL3 device (PAL Technologies Ltd., Scotland, UK) will be worn on the thigh and a CGM (Abbott FreeStyle Libre) will be attached to the upper arm. The research staff will provide: 1) a copy of the informed consent form; 2) instructions with photos and 5 waterproof dressings (Tegaderm) for attaching the activPAL on the thigh; 3) information about the CGM; and 4) daily sleep diary and wear log for 7 days. Participants will receive \$25 for baseline visit 1.

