#### 5.2.1 Baseline assessment

The in-person baseline visit 2 will take place at the VUSN Clinic in the Wesley building. Participants will return the activPAL and the continuous glucose monitoring devices at Baseline visit 2. Participants will receive \$25 for baseline visit 2.

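### The hypoglycaemia procedure gives the glucose-tablet dose in milligrams, almost certainly meaning grams; taken literally, three doses raise blood glucose by about 1 mg/dl at most

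*Combined protocol and SAP*

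**What the plan says.** The procedure is under the heading Protocol for hypoglycemia in section 7.0. It is triggered by symptoms at a visit: "During any study visits, if the study participant develops any of the symptoms below", staff check glucose at once. Below 70 mg/dl, "one of the following options will be administered". The two options are "2 oz (60ml) juice" and "15mg of glucose tables".

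Glucose is re-checked after 15 minutes, and then: "If the glucose level is still below 70mg/dl, the treatment will be repeated up to 2 times". The next sentence confirms that this makes three treatments in all. If glucose is still below 70 mg/dl after them, the PI is notified and the participant is asked to call a healthcare provider. Staff call 911 if the "glucose level is still below 54mg/dl or the participant is unable to function because of mental or physical changes" caused by low glucose.

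The discontinuation criteria in section 7.0 use the same sequence: a glucose below 54 mg/dl after three treatments is a ground for stopping a participant.

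No other section gives a tablet dose or corrects the unit.

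**The concern.** The tablets are offered as an alternative to 60 ml of juice, and either option is meant to bring glucose back to at least 70 mg/dl within three treatments. A dose of 15 mg cannot do that. It is also hundreds of times smaller than the sugar that the juice would plausibly contain. The natural reading is that the writer meant grams. The same line misprints the word for tablets, which also points to hasty typing.

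This is an instruction that a study team member is to carry out, in a trial that enrols only people with type 2 diabetes. Followed literally, the tablet option amounts to no treatment. If each repeat is also followed by a 15-minute wait (the text states the interval only once), up to 3 × 15 = 45 minutes could pass before the step that follows three failed treatments. A participant could also meet the discontinuation criterion because the treatment was inadequate, not because the hypoglycaemia was refractory.

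**Working it through.** The plan derives no figure from the tablet dose, so there is nothing of its own to reproduce. The check is a mass balance on the dose as written.

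**Inputs from the protocol (section 7.0)**
- Dose per treatment: 15 mg.
- Treatments: 1 initial + up to 2 repeats = 3.
- Treatment threshold: 70 mg/dl. The lower threshold, for the 911 call and for discontinuation, is 54 mg/dl.
- Alternative: 60 ml of juice.

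**Assumptions (not in the documents)**
- Distribution volume: 4 to 6 L for whole blood, 15 L for a wider space (12 to 17 L as its range), and 3 L of plasma alone as an extreme.
- Full, immediate absorption and no uptake, so each result is an upper bound for its volume.
- Juice: 8 to 15 g of sugar per 100 ml.

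**Step 1: total literal dose.** 3 × 15 mg = 45 mg.

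**Step 2: largest possible rise.** Rise (mg/dl) = total dose (mg) / volume (dl). The lowest starting value that could reach 70 is 70 minus the rise.

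| Assumed volume | Rise from 45 mg | Lowest start that reaches 70 mg/dl |
|---|---|---|
| 3 L (extreme) | 45/30 = 1.5 mg/dl | 68.5 |
| 4 L | 45/40 = 1.125 mg/dl | 68.9 |
| 6 L | 45/60 = 0.75 mg/dl | 69.25 |
| 15 L | 45/150 = 0.30 mg/dl | 69.7 |

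**Step 3: what a real correction needs.** Going from 54 to 70 mg/dl in 5 L takes at least 16 mg/dl × 50 dl = 800 mg, and 800/15 is about 53 literal doses.

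**Step 4: comparison with the juice option.** 60 ml holds 60 × 0.08 = 4.8 g to 60 × 0.15 = 9 g of sugar. Relative to 15 mg that is 4,800/15 = 320 to 9,000/15 = 600 times as much.

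**Step 5: the same check with grams.** 15 g = 15,000 mg, and 15,000/15 = 1000 times the written dose. One treatment spread through 12 to 17 L gives an upper bound of 15,000/120 = 125 to 15,000/170 = 88 mg/dl before uptake, ample to cross 70. It is also 15/9 = 1.7 to 15/4.8 = 3.1 times the sugar in the juice, so the two options are then of the same order.

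**The case against.** The best case on the other side is that this is a self-evident typing error with little practical reach, and so an editorial matter.

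- **Exposure is small.** The procedure applies only at study visits. Baseline visit 1 is in person (section 5.1: "Those who are eligible for the study will be invited to the in-person visit"), as are baseline visit 2 (section 5.2.1: "The in-person baseline visit 2 will take place at the VUSN Clinic") and the post-intervention visit (section 5.4). The mid-program session is on Zoom (section 5.3.5). A random glucose of 80 to 300 is required before consent at baseline visit 1, so participants start that visit above the treatment threshold. No visit includes an exercise or fasting challenge, and diabetes treatment is not modified.
- **There are safeguards.** Juice is listed first, a failed tablet would show at the re-check, and emergency care is called on low readings or loss of function. Staff would probably read the dose as grams.
- **The replacement figure is inferred.** No section gives a gram dose. The juice comparison supports grams as the order of magnitude, but the number 15 comes only from the printed numeral.
- **The 1 mg/dl figure depends on an assumed volume.** At 3 L it would be 1.5.

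All four points are fair, and they keep this from being rated more seriously. They do not remove it. The tablet option is ineffective at every volume considered. The safeguards limit harm but do not make the written dose work, and the provider-call and discontinuation steps presuppose that three real treatments have been given. Relying on staff to correct the dose silently means that the sensible action departs from the written protocol. The inferred dose is a reason to have it confirmed clinically, not a reason to leave the line alone.

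**Conclusion.** The concern holds. The written tablet dose is almost certainly a milligram-for-gram slip, 1000-fold too small. Three literal doses raise glucose by about 0.3 to 1.1 mg/dl on assumed volumes of 15 L down to 4 L, and by 1.5 mg/dl in the 3 L extreme. Apart from readings within about 1 mg/dl of the threshold (1.5 in that extreme), the tablet option could not restore 70 mg/dl. The volumes are assumptions, but the conclusion is the same for all of them.

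This should be fixed because it is an operative dose in a safety procedure. It is an isolated unit error. Expected harm is limited, and it has no bearing on sample size, estimation or the efficacy analysis.

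**What to change.** Change the line to read 15 g of glucose tablets, which also corrects the misprinted noun, and have the clinically responsible investigator confirm the dose before it is issued. Any staff instruction sheet copied from this section should be corrected at the same time.

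The cost is a correction to one line of the protocol. Design, sample size and analysis are unchanged.
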